## 9.2 ResMed AirSense 10 AutoSet CPAP

The ResMed AirSense 10 AutoSet CPAP is a non-invasive PAP device indicated for the treatment of obstructive sleep apnea in patients weighing more than 30 kg. The device is intended for home and hospital use. It provides a pressure range of 4-20 cm H2O as required to maintain an "air splint" for effective treatment of flow limitation.

The ResMed AirSense CPAP comes in two models, a standard model and an AutoSet for Her model. The devices contain unique algorithms, with the standard model designed to overcome OSA in all patients, Response Setting for mild patients who may have difficulty tolerating high pressures, and the AutoSet for Her designed to treat specific female breathing patterns. All modes are commercially available with CE mark. In this trial, male patients will be given the AutoSet using Response Setting and female patients will be given the AutoSet for Her.

The devices come with in-built humidification and heated tubing which heats and humidifies the air prior to delivery to the patient. A comfortable well-fitting mask will be provided to patients.

**Patients will be requested to use the CPAP (with mask and tubing) every night while sleeping to treat their OSA.**

The participants CPAP will be added to the Trial AirView account for ongoing monitoring during the study.

### 9.3 AirView Wireless Monitoring and MyAir App

Each ResMed AirSense device contains built in wireless connectivity which transmits data via a mobile network tower to a secure data centre. When enabled, data is transmitted at the completion of each period of use (e.g. after each night of use). Data can then be accessed, via a login code, by the patients local sleep service and study team to assess items such as device efficacy (AHI), mask leak, usage hours and CPAP pressure. This data will be viewed by the Trial Sleep therapist, who will intervene if the patient is having issues with therapy or is struggling with compliance (as per section 0).

AirView is compliant with EU 95/46/EC and national privacy laws. Data is encrypted and all database accesses are logged and can be re-traced.

In addition to the AirView computer program, a patient friendly version of the data is available through the ResMed MyAir application. The MyAir application can be accessed via the patient's smartphone and allows the patient to monitor their own treatment data. The MyAir application also provides tips to the patient on things like coping with therapy, managing mask leaks, and adjusting comfort settings. Although the MyAir App is not mandatory in this trial, participants will be strongly recommended to use it to assist their usage of CPAP. However, if patients are unable to use the App they will be shown how to access equivalent information (CPAP device screen + ResMed websites).

#### 9.3.1 Manufacturer Details

The Apnealink Air, AirSense 10 CPAPs, and AirView and MyAir data applications are manufactured by ResMed Ltd, Sydney, Australia

ResMed is a developer, manufacturer and distributor of medical equipment designed for treating, diagnosing, and managing sleep-disordered breathing.

### 9.3.2 Required Training/Experience for Device Use

The PG, APAP and computer software for use in this trial are commercially available and already used in multiple UK locations. Their mode of operation is similar to other commercially available devices, and as such minimal training is required. **Staff at participating centres will undergo standard training on the device equipment, along with training on study procedures.**

## 10 Questionnaires

### 10.1 Short Form 36 (SF-36)

The SF-36 questionnaire is a well validated widely used generic health questionnaire. It was developed as a set of standard, easily administered, quality of life questions for use in routine monitoring and assessment of treatment outcomes in adult patients. The SF-36 measures the limitations of a person's quality of life due to poor health on eight scales: physical activity; social activity; physical health problems; bodily pain; mental health; emotional health; vitality (energy and fatigue); and health perceptions. It takes about 5 minutes to complete.

In this study the Energy and Vitality Component of the SF-36 will be used as the primary outcome, and the entire SF-36 will be used as a secondary outcome.

We have chosen to use a study endpoint of the Energy and Vitality dimension of the SF36, as this has consistently shown to be the most sensitive dimension of the SF-36 for measuring quality of life improvements in mild OSA patients.

### 10.2 Epworth Sleepiness Scale (ESS)

The ESS is a questionnaire used to assess average levels of daytime sleepiness. Patients rate their likelihood to fall asleep in 8 scenarios. The ESS is commonly used in clinic practice to assess for dangerous levels of sleepiness (score of >15) in patients with sleep disorders. It has shown to be a reliable measure of sleepiness with correlation to OSA severity, and sensitivity to post-treatment changes.

### 10.3 Fatigue Severity Scale (FSS)

The FSS is designed to measure the severity of fatigue and how it impacts an individual's daily life in terms of motivation, exercise, daily activity, work, family and social life. It takes 2-3 minutes to complete the 9 scales. The FSS has been used in a number of health conditions, including sleep apnea.

### 10.4 Functional Outcomes of Sleep Questionnaire (FOSQ)

The FOSQ is a questionnaire designed to assess the impact of excessive sleepiness on multiple activities of everyday living. The FOSQ contains 30 items and takes approximately 15 minutes to complete. The FOSQ includes five subscales: activity level; vigilance; intimacy and sexual relationships; general productivity; and social outcomes.

The FOSQ has been shown to be a good instrument for assessing the daily impact of the symptoms of sleep apnea. Studies have found consistent improvements in CPAP groups when using the FOSQ, and it has been recommended for future use when validating the OSA treatments.

## 10.5 Hospital Anxiety and Depression Scale (HADS)

The HADS questionnaire contains 14 items in which patients must choose from a number of four choices to describe their current state of being. It has been found to be a useful tool for validated severity of symptoms of anxiety and depression in both primary care patients and the general population. As anxiety and depression are common in OSA, a specific measure of these conditions is considered important in this study.

## 10.6 Insomnia Severity Index (ISI)

The ISI seven-item questionnaire asks the individual to rate the level of insomnia and perceptions of sleep problems in the last two weeks. Answers must be provided using a scale from 0-4, with 0 reflecting no problem or being very satisfied to 4 indicating a very severe or very dissatisfied experience. Scores are divided into four tiers: 0-7 equates to no clinically significant insomnia, 8-14 equates to sub-threshold insomnia, 15-21 indicates moderate severity insomnia, and 22-28 reflects severe insomnia. Insomnia is frequently reported as a symptom of OSA in female patients, and may also be common in mild OSA patients, therefore, a measure of insomnia has been included as a secondary endpoint in this study.

## 10.7 EQ5D Health Questionnaire

The EQ5D health questionnaire contains several questions relating to health and mobility, the second part of the questionnaire asks the participants how they feel their health is on the day of the visit.

## 10.8 Data Entry

This trial will utilise a web-based, trial database (OpenClinica). OpenClinica is a dedicated and validated clinical trial database designed for data capture. The Chief Investigator will act as Data Custodian for the trial. Relevant ORTU staff will have overview of all entered data.

The trial database is bespoke and hosted on the University of Oxford server with services provided through Oxford University Medical Sciences Division IT Services (MSD IT). The server and database are protected by a number of measures including anti-virus and anti-spyware applications, firewalls, encryption technology and permissions. The database will be backed up on a daily basis.

The database and access to computers are password protected. Paper-based identifiable data at each site will be kept in a locked cabinet, in a locked or ID-access controlled area. The Data Manager will maintain a list of personnel to grant and revoke access

# 11 Sample Size

## 11.1 Sample Size

The required sample size is 224 (112 per group) in the primary outcome group (Mild OSA 2012 classification).

## 11.2 Sample Size calculation

### 11.2.1 Primary Endpoint Calculation

The primary outcome for this evaluation is the Energy and Vitality subscale of the SF-36 questionnaire. Previous clinical trials considering CPAP outcomes in mild OSA patients were reviewed. The MOSAIC study, which has the most similar patient selection criteria, reported an increase in vitality score of 10.8 (SE 1.3) points between baseline and 6 months in the CPAP group, compared with an increase of 4.2 (SE 1.4) in the standard care group. This difference between the treatment groups of 6.6 is considered a significant clinical improvement.

The sample size was calculated using a difference in treatment effect of 6.6 comparing CPAP change between 3 months and baseline (mean change 10.8, SD 17.00) to standard care change between 3 months and baseline (mean change 4.2, SD 18.1) with a 5% significance level and 80% power.

### 11.2.2. Clinical significance of the primary endpoint

A mean change of 6.6 was considered clinically significant by the MOSAIC authors; however a universally agreed clinically significant score change does not currently exist. Minimal Clinically Important Difference (MCID) is a way of calculating the sample size based on the smallest change in a treatment outcome that a patient would identify as important. While a MCID has not been established for treatment of OSA, an expert panel has attempted to define consensus on a change in SF-36 which would be meaningful to a patient with chronic lung disease or asthma. The smallest MCID accepted by the panel was 10 for both COPD and asthma. While it is unclear if these scores can be extrapolated to OSA, this gives a reasonable indication that a score change of 6.6 points in this clinical trial considered to have a positive benefit on patients' lives

### 11.2.3 Sample required to adequately power the primary endpoint.

The sample size calculation shows that 224 randomised patients are required to show a change in energy and vitality in Mild OSA (AASM 2012). However, as participants in this study based on their AASM 2007 scoring classification and then all studies are rescored as per AASM 2012. Therefore an additional number of participants are required to be enrolled in the study.

#### A note about AASM 2007 and 2012 scoring

It is not exactly known how many participants will move from Mild OSA as per AASM 2007 to Mild OSA as per AASM 2012. Previous studies which have rescored sleep studies with different criteria have been reviewed to assist with predictions. The most relevant study, conducted by Bahamman *et al* found that up to 45% of patients would have not been diagnosed with OSA using AASM 2007 criteria, but were diagnosed when using AASM 2012 criteria. In our study we expect a higher rate of participants who score no OSA with AASM 2007 to be diagnosed with OSA using AASM 2012, because these patients have presented at the sleep clinic with symptoms, and other sleep disorders have been excluded.

**Using data from previous trials to estimate occurrences of OSA, we originally predicted that a minimum of 264 participants are would be needed to be enrolled in this study to have the required 224 participants in the Mild OSA (AASM 2012) group for primary analysis. This also allows for a 10% drop-out rate.**

These estimations were checked both after the pilot phase (n = 20), and after 50% of enrolment was complete, and the planned sample size.

Based on this updated data, we anticipate that 300 participants are needed to be recruited in order to meet the required number (224) in Mild OSA 2012 group for primary outcome analysis.

Recruitment will continue until 224 participants are enrolled in the mild OSA group (as per AASM 2012).

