4.6 Sample Size

The sample size of 224 (112 per arm) is based on statistics observed in the MOSAIC study: a mean score difference of 6.6 was observed between 3 months and baseline (considered a significant clinical improvement by the authors of the study) in the Energy and Vitality subscale of the SF-36 questionnaire, with a mean change of 4.2 (SD 18.1) in the Control group and 10.8 (SD 17.0) in the CPAP Treatment group. The sample size calculation is based on a two-sided 5% significance level and 80% power.

It is estimated that approximately 300 participants will need to be randomised in order to reach the required sample size of 224 patients with mild OSA **per AASM 2012 guidelines**. Subjects who are eligible for Home Sleep Testing (HST) are evaluated for their level of OSA. Those patients who have Mild OSA **per AASM 2007 guidelines** are eligible for randomisation. Those patients who have No OSA **per AASM 2007 guidelines** are further assessed based on the AASM 2012 guidelines. All patients with

AHI \geq 5 per AASM 2012 guidelines are also eligible for randomisation. Since the primary endpoint analysis is based on patients with mild OSA per AASM 2012 guidelines, there will be some patients randomised who will not fall into this sample, thus the need for additional enrolment. Additionally, it is expected that 10% of those randomised will drop-out before the end of the study.

The number of patients required to enrol will be reviewed and updated by the Trial Steering Committee (TSC) as new recruitment information accumulates. This will not change the goal of 224 patients completing the study who had mild OSA per the AASM 2012 guidelines.

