5. STATISTICAL METHODS

5.1 Study Populations and Analysis Groups

There are two main study populations in this trial, one group fulfilling the mild OSA AASM 2012 guidelines and the second fulfilling the mild OSA AASM 2007 guidelines. Some trial patients will fulfil both criteria and will therefore be eligible for analysis under both AASM 2007 and AASM 2012. A third study population will consist of patients who fall into the category of Moderate to Severe OSA based on the AASM 2012 guidelines. Patients in this third population will either have tested as No OSA (AHI < 5 e/hr) or Mild OSA based on AASM 2007 guidelines.

The primary endpoint analysis will only be conducted on mild OSA patients per AASM 2012 guidelines. Each secondary endpoint analysis will be carried out on mild OSA patients based on AASM 2012 and AASM 2007 guidelines. Additionally, secondary analyses will be generated descriptively for the subgroup of patients with Moderate to Severe OSA per AASM 2012 guidelines. Therefore, all patients randomised into the trial will be analysed in one or more secondary analyses, with a subset of these patients fulfilling the AASM 2012 guidelines and qualifying for the primary analysis.

The intention to treat (ITT) analysis population will include all randomised patients. The ITT population will be further subdivided as follows:

ITT-1 population includes patients in the ITT with mild OSA per AASM 2012 guidelines.

ITT-2 population includes patients in the ITT with mild OSA per AASM 2007 guidelines.

ITT-3 population includes patients in the ITT with moderate to severe OSA per AASM 2012 guidelines.

The primary endpoint analysis, pool-ability analysis (see Section 5.3) and comparability of baseline characteristics will be generated for the ITT-1 population.

The completed cases (CC) analysis population will be a subset of the ITT population that includes patients who complete the 3-month study visit. [It is possible for there to be missing values for one or more outcome measures in the CC group, if a patient who completes the visits does not complete the questionnaires completely.] The CC population will be further subdivided as follows:

CC-1 population includes patients in the CC with mild OSA per AASM 2012 guidelines.

CC-2 population includes patients in the CC with mild OSA per AASM 2007 guidelines.

CC-3 population includes patients in the CC with moderate to severe OSA per AASM 2012 guidelines.

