5.7 Primary Endpoint Analysis

The primary endpoint measure is the change in the Energy and Vitality subscale of the SF-36 questionnaire from baseline (i.e., pre-treatment) to 3 months post-randomization. It is a continuous variable.

The primary endpoint will be analysed using a mixed-effects repeated measures model to account for missing values. The model will be set up as follows: The Energy and Vitality subscale is the dependent variable, visit (baseline and month 3) is the repeated measure (a fixed effect), subject and site are random effects (with subject nested in site) and treatment group by visit is a fixed effect. In the case that the primary endpoint was not homogeneous across study sites (as discussed in Section 5.3), a treatment by visit by site interaction will also be included in the primary endpoint model as a random effect. Results will be presented as the mean difference in the change score from baseline to 3 months (adjusted for baseline score, as appropriate) between the two treatment groups with a 95% confidence interval at 3 months and p-value for the treatment group effect.

As a sensitivity analysis of the primary endpoint, a similar mixed-effects repeated measures model to the above will be constructed, that also adjusts for other baseline and demographic variables that were found to be imbalanced between treatment groups per Section 5.6. The mean difference in change score from baseline to 3 months will be presented with a 95% confidence interval at 3 months.

For these analyses of the primary endpoint, a P-value of less than 0.05 will be used to indicate statistical significance. Analyses of the primary endpoint will be generated for the ITT-1 population.

A second sensitivity analysis for the primary endpoint will be generated using the CC-1 population.

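### The protocol closes recruitment at 224 mild-OSA (AASM 2012) patients enrolled, the SAP aims for 224 completing; taken literally with 10% loss, the protocol rule gives about 76% to 77% unadjusted power, not 80%

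*Protocol*

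**What the plan says.** The number 224 is attached to three different counts of mild-OSA (AASM 2012) patients.

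- **Randomised.** Protocol 11.2.3: "The sample size calculation shows that 224 randomised patients are required to show a change in energy and vitality in Mild OSA (AASM 2012").
- **Enrolled.** Protocol, note about AASM 2007 and 2012 scoring (the stop rule): "Recruitment will continue until 224 participants are enrolled in the mild OSA group (as per AASM 2012").
- **Completing.** SAP 4.6: "This will not change the goal of 224 patients completing the study who had mild OSA per the AASM 2012 guidelines".

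Drop-out appears in both documents. SAP 4.6 says that "it is expected that 10% of those randomised will drop-out before the end of the study". The protocol note says that the original recruitment forecast of 264 left room for 10% drop-out. It then raises the forecast to 300 without repeating that statement. SAP 4.6 also uses 300: "It is estimated that approximately 300 participants will need to be randomised in order to reach the required sample size of 224 patients".

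The calculation is in Protocol 11.2.1 and is repeated in SAP 4.6: a difference of 6.6 in mean change, SD 17.0 for CPAP, and for control "mean change 4.2, SD 18.1) with a 5% significance level and 80% power". The SAP adds that the test is two-sided.

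**The concern.** If any patient is lost, 224 enrolled cannot become 224 completing. A team working from the protocol and a team working from the SAP would therefore close recruitment at different points, about 25 primary-population patients apart at the expected loss.

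This matters because 224 is the bare result of the formula, with nothing added for loss. It gives 80% power when 224 patients contribute 3-month data. On the same unadjusted basis it gives less when 224 are enrolled and some are lost.

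The protocol's statement that 224 are needed for the primary analysis does not settle which count is meant. The primary analysis set is defined by randomisation and not by completion (SAP 5.1): "ITT-1 population includes patients in the ITT with mild OSA per AASM 2012 guidelines".

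**Working it through.** **Inputs.** Difference 6.6; SDs of change 17.0 and 18.1; 5% level; 80% power (Protocol 11.2.1). Two-sided; 10% drop-out (SAP 4.6). 1:1 allocation (SAP 4.2). The 10% is stated for all randomised patients; applying it to the mild-OSA (2012) subgroup is an assumption. The documents give no correlation between baseline and 3-month scores, so 0.3, 0.5 and 0.7 are assumed.

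**1. Reproduce the plan's figure.**
n per arm = (z₀.₉₇₅ + z₀.₈₀)² × (17.0² + 18.1²) / 6.6² = (1.960 + 0.842)² × 616.61 / 43.56 = 111.1, rounded up to 112, so 224 in total. Noncentral-t power at 112 per arm is 79.97%. The plan's arithmetic is right, and 224 contains no drop-out margin.

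**2. Apply the protocol stop rule literally.**
224 × 0.9 = 201.6 patients with 3-month data, or 100.8 per arm. Noncentral-t power on completers is 75.7%. The difference detectable with 80% power rises from 6.6 to 6.96.

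**3. Credit the planned mixed model.** The model in SAP 5.7 also uses the baselines of patients who drop out. With two visits, equal variances, all baselines observed and 3-month values missing at random at rate d, the variance of the estimated mean change is proportional to
(1 − ρ²)/(1 − d) + (1 − ρ)², against 2(1 − ρ)/(1 − d) for completers only.

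| ρ (assumed), d = 0.10 | variance ratio | effective n per arm | power |
|---|---|---|---|
| 0.3 | 0.965 | 104.5 | 77.1% |
| 0.5 | 0.975 | 103.4 | 76.7% |
| 0.7 | 0.985 | 102.3 | 76.3% |

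**4. Vary the loss (assumed rates).** At 5%: 77.9% on completers, 78.2% to 78.6% with the mixed model. At 15%: 73.2%, and 74.2% to 75.5%.

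**5. Allow for baseline adjustment.** SAP 5.7 says that the difference may be "adjusted for baseline score, as appropriate". Effective adjustment multiplies the change-score variance by (1 + ρ)/2. At 100.8 per arm, power is 90.9%, 86.6% and 82.1% for ρ = 0.3, 0.5 and 0.7. It falls to 80% at ρ ≈ 0.80.

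**6. Enrolment that matches the SAP goal.** 224 / 0.9 = 248.9, so 249 (250 for equal arms). As a share of 300 recruits, 248.9 / 300 = 83.0%. If 300 has no drop-out allowance, the implied share of recruits who are mild by 2012 criteria is 224 / 300 = 74.7%. The documents give neither share.

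**The case against.** The strongest reply is that the stop-rule sentence is loose wording and that drop-out was planned for. The protocol note attaches a 10% allowance to 264, the figure that 300 replaced. SAP 4.6 gives two reasons for recruiting beyond 224: patients who are not mild by 2012 criteria, and drop-out. It then fixes the goal as completers. This largely stands as evidence of intent. It does not repair the rule, because 264 and 300 are forecasts, while the sentence that closes recruitment counts patients enrolled. A generous forecast gives no protection if the stop rule is met first.

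A second reply is that baseline adjustment offsets the loss. It may, as step 5 shows. However, the SAP permits it only where appropriate, no correlation is stated, and both documents calculate from unadjusted change-score SDs.

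A reader might infer more than the documents support:

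- **That the trial is underpowered.** The documents do not show which count closed recruitment. If the SAP goal was met, the calculation's 80% stands.
- **That drop-out was ignored.** Both documents mention it.
- **That aligning with the SAP must exceed the planned 300.** That holds only if 300 contains no drop-out allowance. If it does contain one, the implied mild share is about 83% and 249 enrolled fits. The figure of 300 cannot decide between these readings.

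**Conclusion.** The conflict is real and is in current text. The protocol differs from the SAP on what 224 counts, and its stop rule sits badly with its own drop-out sentence. The intent was probably 224 after drop-out. The sample-size arithmetic itself is correct.

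The consequence is conditional. It needs the stop rule to be applied literally, 10% loss in the mild-OSA (2012) group, and the unadjusted change-score basis of the calculation. Power is then about 76% to 77%, a shortfall of some 3 to 4 points. Effective baseline adjustment could remove the shortfall up to a correlation of about 0.80, an argument that the plan does not make. The point should be corrected because it governs when recruitment to the primary population closes, but it does not undermine the design.

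**What to change.** In Protocol 11.2.3 and the note that follows it, replace the randomised and enrolled counts with the SAP's goal: 224 mild-OSA (2012) patients completing, which is about 249 enrolled at 10% loss. State whether 300 includes drop-out, and the assumed share of recruits who are mild by 2012 criteria.

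What follows, and its cost, depends on what was done:

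- **Recruitment closed with 224 completing.** Only the wording changes. The 80% stands, and a restated lower figure would be wrong.
- **224 enrolled was the rule actually applied.** Restate power as about 76% to 77% at 10% loss, or justify a higher figure by specifying the baseline-adjusted model and its assumed correlation. The cost is wording and possibly a less favourable figure.
- **Recruitment is still open.** The aligned rule enrols about 25 more mild-OSA (2012) patients than the literal one. It fits within 300 if about 83% of recruits are mild by 2012 criteria.

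SAP 4.2 expected recruitment to end on 31 December 2018, and the June 2019 amendment describes the primary analysis as performed. One of the first two cases is therefore the likely one, and the change is a clarification.
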